10.1 Statistical and Analytical Plans (SAP)

A formal SAP will not be performed prior to database lock since this study is a pilot study with no randomization.

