
1- If not previously available (i.e., recent knee MRI within 3 months of screening); if MRI cannot be obtained on the same day due to subject preference and/or MRI scheduling related reasons, MRI can be performed anytime between the baseline visit and intervention visit
 
2- If not previously available (i.e., recent knee radiograph within 6 months of screening). Can be performed on a separate day based on appointment availability or subject's preference.
 
3- Post-procedural MRI can be done on a separate day of visit 6 based on appointment availability and subject's preference as long as it's performed within the timeframe of 3month +/- 10 days.
 
* Visit 1 and 2 can be combined based on subject preference. In that case, procedures listed in visit 2 will be performed after signing informed consent on the same day.
 
** Visit 4 (1-day follow-up) dates range can be +3 days (phone call, telemedicine, or in-person IR clinic visit determined by subject's preference and need for physical examination)
 
*** Visit 8. Optional visit for participants who completed 12 month follow up by August 31, 2024 (by invitation, voluntary, and after obtaining informed consent for this visit). This visit can be performed at any time interval within 18 months – 48 months
								

CONFIDENTIAL

post procedure. This visit can be performed by sending the questionnaire by a safe email and participants can email it back to research coordinator or PI OR by a phone call performed by research coordinator,
	
# 1, 3, 12-month follow-up dates range can be +/- 10 days
	
## The pre-procedural blood work can be done on the day of the procedure prior to performing the procedure based on subject's preference.
	
--	--	--	--

1 Key Roles

- **Principal Investigator (PI):** Will be one of two interventional radiologists performing the procedure. Will be responsible for study integrity, data monitoring, data collection, statistical analysis, and manuscript writing.

[name]

Clinical Assistant Professor of Radiology
Director, Vascular and Interventional Radiology Research Program
Department of Radiology, NYU Langone Health
[name]
[contact]
Email: [contact]

- **Co-PI:** Co-investigator involved in recruiting patients and conducting the clinical assessment for knee osteoarthritis

[name]

Associate Professor
Department of Internal Medicine, NYU Langone Orthopedic Center
[name]

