10.2 Statistical Hypotheses

This is a single arm study (i.e., no sham, placebo or alternative treatment included). The primary objective (clinical success rate) is a binary assessment of whether or not each patient shows at least a 50% reduction in WOMAC pain scores from baseline (pre-treatment) to post-treatment follow-up at 3 months.

The study is designed to test the null hypothesis (H_0) that the true proportion (PT) of patients that will manifest a positive treatment response, is no greater than 0.5 against the one-sided alternative hypothesis (HA) that $PT \geq 0.75$. The null hypothesis will be rejected and it will be concluded that the treatment is worthy of further investigation if at least 16 of the 23 patients show a positive response to treatment.

The response rate will be summarized in terms of the observed proportion of patients manifesting a positive response and a two-sided exact 95% confidence interval (CI) per the Blyth-Still-Casella method (31). The treatment will be declared a success if the data support the conclusion that at least 75% of treated patients can be expected to show a positive response. The treatment will be considered unworthy of additional study without further development if the data are consistent with the conclusion that no more than 50% of treated patients can be expected to show a positive response.

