10.5 Sample Size

The sample size was initially selected based on primary objective so that the study will have 80% power at the 5% significance level for testing the null hypothesis H_0 : $PT \leq 0.5$ against the alternative hypothesis H_A : $PT \geq 0.75$, where PT is the true proportion of patients that will manifest a positive treatment response. As a result, the study will accrue 23 patients since this sample size will endow the test with 80.4% power at a realized significance level of 0.047. with 20% attrition, the study will need 29 patients. We are requesting increase in the sample size to 40. With 20% with 20% attrition, the study will need to enroll 50 patients. The PI and sub-investigators determined that increase in the sample size is necessary to

CONFIDENTIAL

evaluate the role of GAE as a disease-modifying treatment option for knee OA. Since this current study is the only active study in the U.S collecting samples for biomarker analysis and the need for a larger sample size to evaluate changes in biomarker levels, an increase in sample size is needed.

11 Source Documents and Access to Source Data/Documents

Source data is all information, original records of clinical findings, observations, or other activities in a clinical trial necessary for the reconstruction and evaluation of the trial. Source data are contained in source documents. Examples of these original documents, and data records include: hospital records, clinical and office charts, laboratory notes, memoranda, subjects' diaries or evaluation checklists, pharmacy dispensing records, recorded data from automated instruments, copies or transcriptions certified after verification as being accurate and complete, microfiches, photographic negatives, microfilm or magnetic media, x-rays, subject files, and records kept at the pharmacy, at the laboratories, and at medical-technical departments involved in the clinical trial. It is acceptable to use CRFs as source documents. Data collected on electronic CRFs using TrialMaster are attached to this protocol (see attachment 4).

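### No SAP is planned before database lock, although the plan runs a formal one-sided test and leaves open choices that can change its verdict

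*Combined protocol and SAP*

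**What the plan says.** Section 10.1 declines a SAP in advance: "A formal SAP will not be performed prior to database lock since this study is a pilot study with no randomization".

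The same chapter sets up a confirmatory-style test. Under section 10.2 the null is that the true response rate "is no greater than 0.5 against the one-sided alternative hypothesis (HA) that" the rate is at least 0.75. The cutoff is a count, 16 responders out of 23. Once it is reached, the stated consequence is: "The null hypothesis will be rejected and it will be concluded that the treatment is worthy of further investigation". Section 10.5 plans for "80% power at the 5% significance level for testing the null hypothesis" and reports that "this sample size will endow the test with 80.4% power at a realized significance level of 0.047". It then raises the required number from 23 to 40 (50 enrolled) and gives no new cutoff.

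Section 4.1 describes a single-arm, open-label study. Section 1 (Key Roles) says of the PI, who is one of the two operators: "Will be responsible for study integrity, data monitoring, data collection, statistical analysis, and manuscript writing".

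**The concern.** The stated error rate of a cutoff on a count holds only if each patient's status, the denominator and the cutoff are fixed before the count is seen. Being a non-randomized pilot does not remove that condition. With no control arm and no masking, advance rules are the main protection the test has. Here the same person is responsible for both data and analysis, and the plan says that no formal analysis document will exist until after lock. At this sample size, one or two patients near the cutoff decide whether the null is rejected. What is at stake is the conclusion that the treatment merits further study.

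**Working it through.** **1. The plan's own figure.** Inputs from sections 10.2 and 10.5: n = 23, cutoff c = 16, p0 = 0.5, p1 = 0.75.
- Level: P(Bin(23, 0.5) ≥ 16) = 0.0466, stated as 0.047.
- Power: P(Bin(23, 0.75) ≥ 16) = 0.8037, stated as 80.4%.
- Enrolment: 23/0.8 = 28.75, so 29; 40/0.8 = 50.

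All of these reproduce.

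**2. What is fixed and what is open.**
- Fixed: the 50% threshold, the 3-month time point, the null, the exact interval method and a one-line analysis set.
- Responder definition: sections 3.1 and 10.4.1 require the pain reduction and also no rise over baseline in pain-medication use or injection. Sections 4.1, 10.2 and 10.4.2 use the pain reduction alone.
- Cutoff: given only for 23 patients.
- Denominator: section 10.3 keeps only patients who complete every follow-up visit, although the endpoint is at 3 months. Section 5.7.2 allows withdrawn patients to be replaced and does not say how they are counted.
- Patient-level scoring: no rule for missing KOOS items, for a Month-3 visit outside ±10 days, or for missing medication or injection history.

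**3. Cutoff at 40.**
- The smallest cutoff with one-sided level at or below 0.05 is 26: P(Bin(40, 0.5) ≥ 26) = 0.0403, with power 0.946 at 0.75.
- Scaling the old proportion gives 16/23 × 40 = 27.8, so 28: level 0.008, power 0.821.
- A result of 26 or 27 responders passes one rule and fails the other.

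**4. Ambiguous patients.** Suppose m patients cannot be classified by any stated rule, whatever their true outcome, and all are scored as successes. The other n − m must supply c − m responders, so the error is P(Bin(n − m, 0.5) ≥ c − m).

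| Rule | m = 0 | m = 1 | m = 2 |
|---|---|---|---|
| 26 of 40 | 4.0% | P(Bin(39) ≥ 25) = 5.4% | P(Bin(38) ≥ 24) = 7.2% |
| 16 of 23 | 4.7% | P(Bin(22) ≥ 15) = 6.7% | P(Bin(21) ≥ 14) = 9.5% |

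**5. Responder definition.** Take the true composite rate as 0.50 and let dropping the medication/injection condition turn a further share of patients into responders. The documents give no figure for that share, so I assume 2.5%, 5% or 10%. Then P(≥ 26 of 40) is 0.076, 0.133 or 0.317, against 0.040.

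**6. Denominator.** Twenty-six responders among 40 completers give p = 0.040. If the planned 20% attrition (10 of 50) is counted as failure, the same 26 give P(Bin(50, 0.5) ≥ 26) = 0.444.

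**The case against.** The strongest reply is that declining a formal SAP is not the same as having no pre-specification. Section 10 already fixes the elements listed above and names tests for the secondary outcomes. Section 13.2 requires IRB approval before any amendment takes effect. Section 7.3.4.3 states the Month-3 window, and section 11 requires missing CRF data to be explained. Rejecting the null leads only to further investigation, in a self-described pilot. All of this stands, and it confines the concern to the items that section 10 contradicts or omits.

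Three stronger readings are tempting, and the documents do not support them.
- A reader might lower the cutoff by one or two and quote 7.7% and 13.4% (25 or 24 of 40), or 10.5% and 20.2% (15 or 14 of 23). Those are upper bounds. They require that a clear non-responder can always be found and reclassified, which is not what a missing item or a late visit allows.
- A reader might infer that the responder count is on view as it accrues. Section 4.1 says WOMAC is derived from KOOS only at the time of analysis. Staff see the raw answers, but the plan does not produce a running count.
- A reader might infer that the PI personally does every task. Key Roles assigns responsibility; section 4.1 lets the coordinator or an investigator enter data, and section 6.2.1 has either of two radiologists operate. Nothing in the documents shows that any choice was made with results in hand.

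**Conclusion.** The concern holds as a planning defect. Section 10.1 is a stated decision, and its reason does not fit a study with a one-sided null, a count cutoff and a claimed level. Followed as written, the plan leaves verdict-changing choices until outcomes can be known.

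For patient-level scoring the inflation is moderate: to 5.4% or 7.2% at 26 of 40, and to 6.7% or 9.5% at 16 of 23. This assumes one or two ambiguous patients, always resolved toward success; the documents do not say how many there would be. The larger exposure comes from the definition and the denominator. Its size depends on the assumed reclassification share and on counting the 10 non-completers as failures. The 26-of-40 cutoff is my calculation, since the plan gives none for 40.

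**What to change.** Replace section 10.1 with:

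> A SAP will be signed and dated before database lock and before any tabulation of 3-month response. It fixes: one responder definition (the composite in sections 3.1 and 10.4.1); the exact cutoff for the current sample size (at least 26 of 40; one-sided alpha 0.040, power 0.946 at a true rate of 0.75); the 3-month analysis set, including the handling of withdrawn and replaced patients; and the scoring of missing KOOS items, out-of-window Month-3 visits and missing medication or injection history. Any later change is reported as post hoc.

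Sections 4.1, 10.2, 10.3 and 10.4.2 should then be aligned with it. Completing section 10 itself by dated amendment before lock would serve equally well; the timing and content matter more than the form.

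The cost is a few pages written earlier and the loss of freedom to choose after lock. No patient, visit or data item changes.

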10.2 Statistical Hypotheses

This is a single arm study (i.e., no sham, placebo or alternative treatment included). The primary objective (clinical success rate) is a binary assessment of whether or not each patient shows at least a 50% reduction in WOMAC pain scores from baseline (pre-treatment) to post-treatment follow-up at 3 months.

The study is designed to test the null hypothesis (H_0) that the true proportion (PT) of patients that will manifest a positive treatment response, is no greater than 0.5 against the one-sided alternative hypothesis (HA) that $PT \geq 0.75$. The null hypothesis will be rejected and it will be concluded that the treatment is worthy of further investigation if at least 16 of the 23 patients show a positive response to treatment.

The response rate will be summarized in terms of the observed proportion of patients manifesting a positive response and a two-sided exact 95% confidence interval (CI) per the Blyth-Still-Casella method (31). The treatment will be declared a success if the data support the conclusion that at least 75% of treated patients can be expected to show a positive response. The treatment will be considered unworthy of additional study without further development if the data are consistent with the conclusion that no more than 50% of treated patients can be expected to show a positive response.

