5.6 Total Number of Participants and Sites

Data from 40 participant will be required and the study would accrue 50 patients to account for an attrition rate of 20%.

The study will be conducted only at NYULH Hospitals. No subjects will be enrolled at external national or international sites.

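### The rejection rule in section 10.2 is still 16 of 23 responders, although the plan now requires data from 40 patients and gives no cutoff for that number

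*Combined protocol and SAP*

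**What the plan says.** Section 10.2 tests a true response rate of at most 0.5 against a one-sided alternative of 0.75 or more. Its only numerical rule is that the treatment is "worthy of further investigation if at least 16 of the 23 patients show a positive response to treatment". The rule is in the present tense and is not marked as historical.

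Section 10.5 explains where 23 came from. The size was first chosen to give "80% power at the 5% significance level for testing the null hypothesis", and "this sample size will endow the test with 80.4% power at a realized significance level of 0.047"; with 20% attrition this meant 29 patients. The section then says "We are requesting increase in the sample size to 40", or 50 enrolled. The reason given is biomarker evaluation and the possible disease-modifying role of the procedure. No cutoff, alpha or power follows for 40.

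Section 5.6 states "Data from 40 participant will be required and the study would accrue 50 patients to account for an attrition rate of 20" percent. The Protocol Summary and section 4.1 agree, and section 5.4 says that the 40 are needed for the primary objective.

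Three other statements bear on the point. Section 10.1 says that no formal SAP will be prepared. Section 10.2 plans a two-sided exact 95% interval (Blyth-Still-Casella) and calls the treatment unworthy of more study if the data are consistent with a response rate of no more than 50%. It also sets a separate criterion for declaring success, namely support for a response rate of at least 75%.

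**The concern.** The count that decides rejection refers to a group the current plan no longer defines. Nothing says that the primary test stays with the first 23 patients, and nothing converts the rule to 40. With no SAP planned, no later document is due to settle it.

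What is at stake is the go/no-go conclusion of the study's only powered test. With 26 or 27 responders among 40, the null is rejected under a cutoff re-derived at the plan's own 5% level, but not if the 16/23 proportion is carried over. The trial is open-label, and section 1 gives the principal investigator responsibility for data collection and statistical analysis. An undefined cutoff therefore leaves room to settle the reading after results are known.

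**Working it through.** **Inputs.** Null rate 0.5 and alternative 0.75, one-sided (10.2); significance level 5% and target power 80% (10.5); cutoff 16 of 23 (10.2); revised number 40, with 50 enrolled at 20% attrition (5.6, 10.5).

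**Formula.** For a cutoff of r responders among n, alpha = P(X ≥ r | n, 0.5) and power = P(X ≥ r | n, 0.75), with X binomial.

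**The plan's own figures.** For 16/23, alpha = 0.0466 and power = 0.8037, which match the stated 0.047 and 80.4%. No smaller n reaches 80% power with an exact one-sided 5% test. Attrition: 23/0.8 = 28.75, so 29; 40/0.8 = 50. All the stated figures are correct for n = 23.

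**Cutoffs for 40.**

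| Cutoff | alpha | power at 0.75 |
|---|---|---|
| 25/40 | 0.0769 | 0.9738 |
| 26/40 | 0.0403 | 0.9456 |
| 27/40 | 0.0192 | 0.8968 |
| 28/40 | 0.0083 | 0.8209 |

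The smallest count with alpha at most 0.05 is 26. Carrying over the proportion gives 40 × 16/23 = 27.8, so 28. The same search gives 29/45 (alpha 0.036) and 32/50 (alpha 0.033).

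**Both rules used without adjustment (hypothetical).** Let X be the responders among the first 23 and Y those among the next 17. Under a rate of 0.5, P(X ≥ 16) + Σ over x ≤ 15 of P(X = x) × P(Y ≥ 26 − x) = 0.068.

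**Agreement with the planned interval.** The Blyth-Still-Casella interval treats the two tails symmetrically at 0.5, so whether it contains 0.5 depends on the smallest symmetric region with probability of at least 0.95.
- n = 40: counts 15 to 25 have probability 1 − 2 × 0.0403 = 0.919, which is too small. Counts 14 to 26 have 1 − 2 × 0.0192 = 0.962. A result of 26 is therefore compatible with 0.50, and 27 is not.
- The Clopper-Pearson lower limits agree. The 2.5% quantile of Beta(26, 15) is 0.483 and that of Beta(27, 14) is 0.509.
- n = 23: counts 8 to 15 have probability 1 − 2 × 0.0466 = 0.907, so 16/23 is also compatible with 0.50. The mismatch is present in the existing rule too.

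**The case against.** The strongest defence is that section 10.5 labels the 23-patient calculation as initial and gives biomarkers as the reason for the increase, so the primary test might have been meant to stay as it was. The label does cover the alpha and power in 10.5, which are correct for what they describe. It does not cover the cutoff in 10.2, and section 5.4 assigns the 40 patients to the primary objective. If only the first 23 were intended, the plan would have to say so and define them.

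A second defence is that the exact interval applies at any n, so inference against 0.5 remains possible. That stands as partial mitigation. However, the interval is not stated as the rejection rule, and it disagrees with a one-sided 5% cutoff at the margin.

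Stronger readings are tempting, and the documents do not support them:
- *The type I error is inflated.* The three credible readings all have alpha below 5%. The figure of 0.068 needs a second test, and none is planned.
- *Sixteen responders among 40 would suffice (alpha 0.92).* The text says 16 of 23, so this is not a credible reading.
- *The trial's confirmatory claim depends on this rule.* The study is a pilot, the rule supports only further investigation, and success has its own 75% criterion.
- *The sample-size arithmetic is wrong, or power was lost.* The arithmetic reproduces, and power rises to 94.6% with 26/40.

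**Conclusion.** The point holds as an amendment that was not carried through. The only operative cutoff belongs to 23 patients while the plan calls for 40, and the number of responders needed among 40 is undefined. A re-derived cutoff and a carried-over proportion differ by two responders (26 against 28), with alpha 0.040 against 0.008 and power 0.946 against 0.821.

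The harm is an undefined go/no-go rule, with no demonstrated error inflation. It needs correcting before analysis because no other document will supply the rule. The figures assume independent binomial responses, rates of 0.5 and 0.75, and exactly 40 patients analysed. The documents do not show whether the 23-patient rule has ever been applied.

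**What to change.** Before the primary outcomes are examined:

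1. Replace the rule in 10.2 with the smallest count whose exact one-sided binomial alpha is at most 0.05 for the number analysed. Give 26/40 as the planned case (alpha 0.040, power 94.6% at 0.75), with 29/45 and 32/50 as examples for other totals.
2. State in 10.2 that 16 of 23 is withdrawn, and update 10.5 with the cutoff, alpha and power for 40.
3. Define the number analysed. Section 10.3 currently admits only participants who complete all follow-up visits, although the primary outcome is at 3 months.
4. Reconcile the cutoff with the two-sided 95% interval and the 50% wording. Either adopt 27/40 (alpha 0.019, power 89.7%), which excludes 0.50, or keep 26/40 and state which criterion governs when the interval still includes 0.50.
5. Keep the 75% success criterion visibly separate from this rule.

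The cost is a wording amendment to 10.2, 10.3 and 10.5. No extra patients are needed, and power at 0.75 stays above the 80% target under either cutoff.

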Population	40 patients, age 30-80, any gender, with grade 2,3, or 4 (in select subjects with no bone deformity) knee OA on the most recent knee radiographs obtained within 6 months of intervention

CONFIDENTIAL

Study Sites	Single center: NYU Langone Health Hospitals
Number of participants	Data from 40 patients will be required The study would accrue 50 patients to account for an attrition rate of 20%
Description of Study Agent/Procedure	Embozene™ Color-Advanced Microspheres are spherical, tightly calibrated, biocompatible, non-resorbable, hydrogel microspheres coated with an inorganic perfluorinated polymer used for embolization.
Key Procedures	Transcatheter arterial embolization of one or more genicular artery(ies) using Embozene™ Color-Advanced Microspheres
Statistical Analysis	The primary objective is to assess the clinical success rate, which will be summarized in terms of the observed proportion of patients manifesting a positive response and a two-sided exact 95% confidence interval (CI) per the Blyth-Still-Casella method (reference). The treatment will be declared a success if the data support the conclusion that at least 75% of treated patients show a positive response.

Schematic of Study Design

Prior to Enrollment

[figure not shown]
Day 0

Day 1

[figure not shown]
Day 30

Day 90

Day 360

CONFIDENTIAL

This material is the property of the NYU School of Medicine and Langone Medical Center. Do not disclose or use except as authorized in writing by the study sponsor
Interventional Template Version: 12 February 2020

Schedule of Activities

Visit #	Visit 1*	Visit2*	Visit 3	Visit 4**	Visit 5*	Visit 6*	Visit 7*	Visit 8***
Visit Description	Screening	Baseline	Intervention	1-day follow-up	1-month follow-up	3-month follow-up	12-month follow-up	>12 months
Eligibility screen	X							
Informed consent	X							
Demographics		X						
Medical history		X						
Adverse Events				X	X	X	X	X
Physical exam		X		X	X	X	X	X
Medication History		X			X	X	X	X
Pain VAS**		X			X	X	X	X
KOOS score		X			X	X	X	X
EQ-5D-5L scale		X			X	X	X	X
Previous treatments		X			X	X	X	X
Venous blood draws		X##	X##		X	X	X	X
Urine samples		X			X	X	X	X
Knee MRI		X ¹				X ³		
Knee radiograph		X ²						
Genicular artery embolization			X					

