10.4 Description of Statistical Methods

The response rate will be summarized in terms of the observed proportion of patients manifesting a positive response and a two-sided exact 95% confidence interval (CI) per the Blyth-Still-Casella method (31).

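### Success is declared at a response rate of at least 75%, but the only test defined and powered is of 50% or less, and the 75% rule has no cutoff

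*Combined protocol and SAP*

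**What the plan says.** Section 10.2 makes three decision statements about one binary endpoint.

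- **Worthy.** The null is that the true proportion of responders "is no greater than 0.5 against the one-sided alternative hypothesis (HA) that" it is at least 0.75. On rejection the treatment is "worthy of further investigation if at least 16 of the 23 patients show a positive response to treatment".
- **Success.** "The treatment will be declared a success if the data support the conclusion that at least 75% of treated patients can be expected" to respond. The Statistical Analysis row of the Protocol Summary gives only this rule: "The treatment will be declared a success if the data support the conclusion that at least 75% of treated patients show a positive response".
- **Unworthy.** The treatment does not merit further study as it stands "if the data are consistent with the conclusion that no more than 50% of treated patients can be expected to show a positive response".

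Only the first has a number. The response rate is to be summarized with a "two-sided exact 95% confidence interval (CI) per the Blyth-Still-Casella method" (10.2, 10.4, 10.4.1). Section 10.5 sizes the study for the test of 0.5 alone: 80.4% power and a realized level of 0.047 with 23 patients. It then raises the target to 40 evaluable and 50 enrolled. Section 10.1 says no formal SAP will be written before database lock.

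**The concern.** The 75% figure has two roles. In 10.5 it is the alternative at which power was calculated. In the success sentence it is a value that the data must support. These are different hypotheses, and a trial sized for the first has no planned ability to meet the second.

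Because the success sentence gives no criterion, several readings are open and their chances of success differ widely. The Summary, which most readers see first, carries only this sentence. The study is open-label and single-arm (4.1), the principal investigator is responsible for the statistical analysis (section 1), and no later SAP is planned to settle the meaning. The reading could therefore be chosen after the data are seen.

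A smaller point concerns the unworthy rule. The test is one-sided at 5%, while the only interval named is two-sided at 95%. The two can disagree at the edge of the rejection region.

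**Working it through.** **Inputs.** Null 0.5, alternative 0.75, cutoff 16 of 23, two-sided 95% exact interval (10.2). One-sided 5% level, 80% target power, current evaluable number 40 (10.5). X is the number of responders, binomial(n, p).

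**1. The plan's own figures.** With n = 23:
- P(X ≥ 16 | p = 0.5) = 0.0466, stated as 0.047.
- P(X ≥ 16 | p = 0.75) = 0.8037, stated as 80.4%.

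Both reproduce, and both describe a test of 0.5. The cutoff proportion is 16/23 = 0.696, below 0.75.

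**2. The same test at n = 40.** The cutoff is the smallest k with P(X ≥ k | 0.5) ≤ 0.05. For k = 25 the tail is 0.077 and for k = 26 it is 0.040, so k = 26. Power is P(X ≥ 26 | 0.75) = 0.946.

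**3. What supporting at least 75% could mean at n = 40.**

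| Reading | Count needed | Basis | Probability at true 0.75 | Probability at true 0.90 |
|---|---|---|---|---|
| Two-sided 95% lower limit above 0.75 | 36 | Clopper-Pearson lower limit 0.732 at 35, 0.763 at 36 | 1.6% | 63% |
| One-sided 5% test of PT ≤ 0.75 | 35 | one-sided lower limit 0.725 at 34, 0.755 at 35 | 4.3% | 79% |
| Point estimate of at least 75% | 30 | 30/40 = 0.75 | 58% | 99.9% |
| For comparison: reject PT ≤ 0.5 | 26 | step 2 | 94.6% | above 99.9% |

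A Blyth-Still-Casella-type interval also first exceeds 0.75 at 36 (lower limit 0.757 to 0.780, depending on how ties between acceptance sets are broken).

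**4. The boundary of the unworthy rule.**
- *n = 23.* At p = 0.5 the shortest acceptance set with 95% coverage has 10 points, and the only one is 7 to 16 (coverage 0.965). So the interval for 16/23 contains 0.5; Clopper-Pearson gives 0.471 to 0.868. At 17/23 the Clopper-Pearson lower limit is 0.516.
- *n = 40.* The symmetric shortest set at p = 0.5 is 14 to 26, so the interval for 26/40 contains 0.5; Clopper-Pearson gives 0.483 to 0.794. At 27/40 the Clopper-Pearson lower limit is 0.509.
- *A caveat on n = 40.* Two other 13-point sets also reach 95% (13 to 25 and 15 to 27, coverage 0.951 each). The Blyth-Still-Casella-type lower limit at 27/40 is therefore 0.498 to 0.500, depending on the tie convention.
- *How often.* P(X = 26 | n = 40) = 0.946 − 0.897 = 0.049 at a true 0.75, and 0.040 − 0.019 = 0.021 at a true 0.5.

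**The case against.** **Two tiers.** Worthy and success are different labels and may be meant as a lower and a higher tier. A pilot result that justifies further study without establishing 75% is then no contradiction. This stands. At a true rate of 0.75, the chance of 26 to 35 responders, where PT ≤ 0.5 is rejected but the two-sided lower limit stays at or below 0.75, is 0.946 − 0.016 = 0.930. A reader might infer that the conclusion is indeterminate over most of the likely results. The text does not support that, because under two tiers those results are simply worthy. It does leave the upper tier without a criterion.

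**One rule restated.** Since the formal alternative is written as PT ≥ 0.75, the success and unworthy sentences may only restate accepting the alternative and retaining the null. There would then be a single rule and no conflict. The inference would still be wrong, because rejecting 0.5 does not establish 0.75.

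**Low probability by construction.** Any valid 5% test of PT ≤ 0.75 succeeds at most 5% of the time when the rate is exactly 0.75. This also stands. A reader might infer that the trial has almost no chance of success, but that holds only if support means a confidence limit or test against 0.75. On the point-estimate reading the chance is 58%.

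**Three labels at once.** A reader might infer that the same result will be worthy, not a success and unworthy together. The plan uses the interval to summarize the response rate and nowhere makes it the test for unworthy. If consistent with no more than 50% means failing the one-sided test (15 or fewer of 23), worthy and unworthy are exact complements. The overlap needs the interval reading, and is then confined to the boundary.

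**Conclusion.** The concern holds for the 75% rule. The declared success criterion does not follow from the test defined in 10.2 or the power calculation in 10.5, and it has no cutoff. With 40 analysed and a true rate of 0.75, the chance of meeting it runs from 1.6% to 58% depending on an unstated reading, against 94.6% for the test that the trial was sized for. These figures assume exactly 40 analysed patients and independent binary responses.

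The overlap of worthy and unworthy is secondary. It exists only if the unworthy rule is read through the two-sided 95% interval, and then at the boundary count: 16/23, or 26/40, the latter with probability 4.9% at a true 0.75. At 40 patients one tie convention for the Blyth-Still-Casella interval also puts the lower limit at 27/40 marginally below 0.5.

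That 10.2 still states its cutoff for 23 patients although the target is now 40 is a related but separate matter.

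**What to change.** 1. In 10.2, make the exact one-sided 5% test of PT ≤ 0.5 the only decision rule. Define the cutoff as the smallest count with exact one-sided p ≤ 0.05 for the number actually analysed. For 40 this is 26 (level 0.040, power 0.946). The general wording is needed because 10.3 analyses those who complete all visits, up to 50 may be enrolled, and 5.7.2 allows replacement, so the number may not be 40. With 50 analysed, for example, P(X ≥ 31 | 0.5) = 0.059 and P(X ≥ 32 | 0.5) = 0.032, so the cutoff would be 32.
2. Define unworthy as failing that test.
3. Describe 0.75 only as the design alternative. Remove or reword the success sentence in 10.2 and in the Protocol Summary. If the sponsor wants a higher tier, label it descriptive and state its cutoff and the probability of reaching it.
4. Report the one-sided 95% exact (Clopper-Pearson) lower limit with the decision, since it inverts the same test (0.508 at 26/40). In 10.2 and 10.4, keep the two-sided Blyth-Still-Casella interval and label it descriptive.

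The cost is wording in 10.2, 10.4 and the Summary; no patients or data are added. The downside is that the formal claim becomes a response rate above 50%, not of at least 75%.
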